10 STATISTICS

10.1 Sample size

The trial sample size was calculated to achieve 80% power to reject the null hypothesis $H_0 = "r \leq 70\%"$, using a one-sided exact binomial test with 5% alpha risk.

From historical clinical data, the true response rate is expected to be greater than 90%. However, to remain conservative the true response rate could only be estimated from localized intermediate-risk prostate cancer patients patients who underwent the TOOKAD Soluble procedure and for whom biopsies were available after 12 months. Using these conservative estimates we identified a true response rate is greater than 83.6% with >80% posterior probability (assuming a beta-binomial model).

Using this conservative choice for true response rate $r=83.6\%$ a minimum of $N=44$ patients with fully evaluable data is required.

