#### **Planned sample size**

For an assumed true response rate of 83.6%, we can discount a response rate of 70% at a one-sided alpha of 10%, with a power of 80% if we have a sample size of 44 patients.

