### **Primary efficacy analysis**

The proportion of patients with no pattern 4 or 5 found in the 12 month biopsy will be reported along with a one-sided 90% confidence interval. Patients who have pattern 4 or 5 found before 12 months and who receive radical therapy will be treated as treatment failures. The treatment will be considered a success if the lower bound, rounded to 0.01, is 70% or higher. For a sample size of 44, this means that treatment will be declared a success if 35 or more patients respond.

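### The SAP's 35-of-44 success cut-off has a type I error of 10.9%, above its own 10%, because the lower confidence bound is rounded up to 70%

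*SAP*

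**What the plan says.** The SAP section on planned sample size starts from "For an assumed true response rate of 83.6"% and states that "we can discount a response rate of 70% at a one-sided alpha of 10%, with a power of 80"%. The number it gives for this is 44.

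Its primary efficacy analysis says the proportion without pattern 4 or 5 at month 12 "will be reported along with a one-sided 90% confidence interval". No interval method is named. The decision rule follows: "The treatment will be considered a success if the lower bound, rounded to 0.01, is 70% or higher". The SAP then gives the rule as a count: "For a sample size of 44, this means that treatment will be declared a success if 35 or more patients respond".

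Protocol section 10.1 uses the same 44 patients, the same 83.6% and the same null hypothesis (response rate of 70% or less), but "using a one-sided exact binomial test with 5% alpha risk".

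**The concern.** The null hypothesis covers every response rate up to and including 70%. A lower bound below 70% does not exclude it, and rounding that bound to two decimals does not change what the data show. If the printed cut-off is reached only through rounding, the rule's real false-positive rate could exceed the SAP's 10%, and the stated 80% power could depend on that excess.

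This is the only success criterion for the primary endpoint, in a single-arm trial with no control group to fall back on. With exactly 35 responders out of 44, the sponsor would report that 70% had been excluded, although the exact one-sided p-value would be 0.109.

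**Working it through.** **Inputs.** Null rate 0.70, assumed true rate 0.836, one-sided alpha 10%, power 80%, N = 44 (SAP, planned sample size). Cut-off 35 of 44 and a one-sided 90% bound rounded to 0.01 (SAP, primary efficacy analysis). 50 patients are to be included so that at least 44 are evaluable (protocol synopsis, number of patients).

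**1. Reproducing N = 44.** The one-sample normal approximation gives

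N = [(z₀.₉₀·√(0.70·0.30) + z₀.₈₀·√(0.836·0.164)) / (0.836 − 0.70)]² = [(1.2816·0.4583 + 0.8416·0.3703) / 0.136]² = 43.7, so 44.

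The SAP's sample size is therefore consistent with an approximate calculation at one-sided 10%.

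**2. Reproducing the cut-off of 35.** The Clopper-Pearson one-sided 90% lower bound for r responders in n is the 10th percentile of a Beta(r, n − r + 1) distribution.

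| Responders of 44 | Lower bound | Rounded to 0.01 | SAP rule |
|---|---|---|---|
| 34 | 0.6716 | 0.67 | fails |
| 35 | 0.6964 | 0.70 | passes |
| 36 | 0.7215 | 0.72 | passes |

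The exact bound plus rounding gives the printed cut-off of 35. Without rounding, the cut-off is 36.

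**3. Error rates of the cut-offs at n = 44.** Size is P(X ≥ c) for X ~ Binomial(44, 0.70). Power is the same probability at 0.836.

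| Cut-off c | Size | Power |
|---|---|---|
| 35 (SAP) | 10.92% | 82.6% |
| 36 | 5.64% | 71.1% |
| 37 | 2.55% | 56.4% |

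The size of the SAP rule, 10.9%, depends only on the printed count and not on how the interval is computed. The largest attainable size that does not exceed 10% is 5.6%, at 36 of 44, where power is 71.1%. The smallest N with exact size at most 10% and power at least 80% is 45 (cut-off 36, size 9.3%, power 80.7%).

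**4. Other numbers analysed.** For n from 40 to 50 with the exact bound, rounding lowers the cut-off at three values only.

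| n | Cut-off with rounding | Size | Cut-off without rounding | Size |
|---|---|---|---|---|
| 40 | 32 | 11.1% | 33 | 5.5% |
| 44 | 35 | 10.9% | 36 | 5.6% |
| 48 | 38 | 10.7% | 39 | 5.7% |

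At the other sizes in this range rounding changes nothing and the exact size stays at or below 9.4%. With 50 analysed the cut-off is 40 either way, with size 7.9% and power 81.3%. So wherever the rounding clause has an effect in this range, it takes the error rate above 10%.

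**The case against.** The strongest reply has four parts.

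- **Interval method.** The SAP does not name one. With approximate intervals 35/44 passes unrounded (Wald 0.718, Wilson 0.708, Jeffreys 0.709, mid-P 0.708), so rounding would not be the cause. This stands as a limit on attribution. The exact method is an inference: the protocol specifies an exact binomial test, and only under an exact bound does the rounding clause admit 35. The 10.9% does not depend on it.
- **Size of the excess.** It is 0.9 percentage points and comes from discreteness: the attainable sizes at 44 jump from 5.6% to 10.9%. The rule and its count are openly pre-specified. This is fair, and it means that only a result of exactly 35 of 44 changes the decision. It does not make the stated 10% true.
- **Dependence on n.** 44 is a minimum out of 50, and at most nearby sizes rounding has no effect. This is also correct, but 44 is the number for which the SAP states its alpha, its power and its cut-off.
- **Comparison with the protocol's 5%.** Most of that gap comes from the SAP's move to 10%, not from rounding. Even 36 of 44 has size 5.6%, above 5%. The disagreement between the documents is a separate and larger question, and the present point does not rely on it.

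**Conclusion.** The concern holds. The primary success rule, as printed, has an exact type I error of 10.9% at a true rate of 70%, against the SAP's 10%. At 44 patients the SAP can have exact control at 10% with 71.1% power, or 82.6% power with 10.9% error, but not 10% with 80%.

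The 10.9% rests only on the printed cut-off and the binomial model. That rounding is the cause rests on reading the unnamed interval as Clopper-Pearson, which fits both the protocol's test and the printed cut-off. The excess is modest and is confined to n = 40, 44 and 48 within 40 to 50, but it affects the threshold on which the trial's primary claim depends.

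Measured against the protocol's 5%, the SAP rule has more than twice the stated error (10.9/5 = 2.2). The SAP's closing section on changes from the protocol lists no change of alpha.

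**What to change.** In the SAP's primary efficacy analysis:

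- Delete the rounding clause. State that the bound is the one-sided 90% Clopper-Pearson lower limit and that its unrounded value must exceed 70%.
- Replace 35 with 36 of 44, and give the cut-off for each number analysed: 36 for 44, 36 for 45, 37 for 46, 38 for 47, 39 for 48, 39 for 49 and 40 for 50.
- In the planned sample size section, restate the power at 44 as 71%. If 80% is to be kept at 10% alpha, 45 analysed patients is the smallest number that gives it (80.7%). Exact power then drops below 80% at 46 to 48 (78.7%, 76.7%, 74.6%) and is above it again at 49 and 50 (83.1%, 81.3%). All of these lie within the 50 patients already planned.
- Settle whether alpha is 5% or 10%, and record any departure from the protocol in the section on changes. If 5% is kept, the cut-off at 44 is 37, with power 56.4%.

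At 10% alpha the cost is a change of SAP wording, one more responder required at n = 44 (and at 48), and a lower stated power. No new patients or procedures are needed. The change should be made before the month 12 results are known, because moving the threshold after seeing 35 of 44 would not be credible.

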### **Secondary efficacy analysis**

#### **Biopsy results**

Biopsy results at each follow-up (3, 12, 24, 36, 48 and 60) for each definition of positive biopsy will be given as cumulative frequency, along with 95% C.I., with radical therapy as a competing risk. The alternative definitions of positive biopsy are:

1. Presence of any pattern 4 or 5 disease (primary endpoint)
2. Presence of cancer of any grade
3. Presence of any pattern 4 or 5 disease in the treated lobe
4. Presence of cancer of any grade in the treated lobe

Analyses will be repeated with radical treatment counted as an event. As retreatment at 3 months is allowed, 3 month results will be treated as a binary endpoint with 95% C.I. presented in a table.

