### **Secondary endpoints**

- Binary response to treatment defined as the absence of any Gleason grade 4 or 5 biopsy on or before months 24, 36, 48 and 60. If a subject is retreated following a positive biopsy at 3 months and subsequent biopsy shows absence of Gleason grade 4 or 5, the subject will be considered to have responded
- Binary response to treatment defined as the absence of any Gleason grade 4 or 5 biopsy on or before months 12, 24, 36, 48 and 60 in the treated lobe. If a subject is retreated following a positive biopsy at 3 months and subsequent biopsy shows absence of Gleason grade 4 or 5, the subject will be considered to have responded
- Binary response to treatment defined as the absence of any prostate cancer on biopsy on or before months 3, 12, 24, 36, 48 and 60. If a subject is retreated following a positive biopsy at 3 months and subsequent biopsy shows absence of any cancer, the subject will be considered to have responded
- Binary response to treatment defined as the absence of any prostate cancer on biopsy on or before months 3, 12, 24, 36, 48 and 60 in the treated lobe. If a subject is retreated following a positive biopsy at 3 months and subsequent biopsy shows absence of any cancer, the subject will be considered to have responded
- Changes in biopsy result between 3, 12, 24, 36, 48 and 60 months after the procedure
- Patients' reported outcome measures (PROMs) impairment: urinary symptoms using IPSS and erectile functions using IIEF prior to treatment beginning and then 1, 3, 6, 12, 24, 36, 48 and 60 months after completing treatment.

Quality of life is assessed using validated questionnaires. The IPSS comprises seven questions on the urinary symptoms plus one general question about the QOL related to urinary symptoms, whereas the IIEF comprises 15 questions. For both questionnaires, patients self-rate their responses: for the IPSS, using a six-point scale where 0 indicates 'none' or 'normal', whereas 5 indicates the worst response; for the

IIEF, using a five- or six-point scale where 0 indicates 'no sexual activity', and 5 indicates the best response (questions 1 to 10), or where 1 indicates the worst response and 5 the best response (questions 11 to 15).

- Rate of adverse events following treatment

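### The SAP is inconsistent on whether Month 3 positives enter the cumulative biopsy curves, and neither reading yields the secondary endpoints as defined

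*SAP*

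**What the plan says.** Under Biopsy results, the SAP begins: "Biopsy results at each follow-up (3, 12, 24, 36, 48 and 60) for each definition of positive biopsy will be given as cumulative frequency", "with radical therapy as a competing risk". Four definitions of a positive biopsy follow: pattern 4 or 5, or any cancer, each for the whole gland and for the treated lobe. The section then adds: "Analyses will be repeated with radical treatment counted as an event". It ends with: "As retreatment at 3 months is allowed, 3 month results will be treated as a binary endpoint with 95% C.I. presented in a table".

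Under Secondary endpoints, response is cumulative. The whole-gland pattern 4/5 version reads: "Binary response to treatment defined as the absence of any Gleason grade 4 or 5 biopsy on or before months 24, 36, 48 and 60". The treated-lobe version of that endpoint also lists Month 12, and the two any-cancer versions list Months 3 and 12. Each version has one exception, worded for pattern 4/5 as: "If a subject is retreated following a positive biopsy at 3 months and subsequent biopsy shows absence of Gleason grade 4 or 5", in which case the man counts as a responder.

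Under Primary efficacy analysis, the SAP says: "Patients who have pattern 4 or 5 found before 12 months and who receive radical therapy will be treated as treatment failures".

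Two further rules decide who is in the curves. The SAP's Efficacy population requires data at the 12 month biopsy, and its Efficacy analysis section applies that population to all efficacy analyses.

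**The concern.** The first and last sentences of Biopsy results pull in different directions. The first puts Month 3 in the cumulative frequency. The last gives Month 3 a separate binary treatment and does not say whether a Month 3 positive is also an event in the curve. Its stated reason, retreatment, concerns only the retreated men.

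Men with a positive Month 3 biopsy who are not retreated are foreseeable. Retreatment is allowed, not required (protocol 4.1 and 6.4.10). Protocol 5.5.4 withdraws certain Month 3 positives to standard care, and 6.4.11 lets any man choose radical therapy at any time. For these men the endpoint definition is clear: a positive on or before the month in question is non-response, because the exception needs retreatment.

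At stake are the main long-term curves for all four definitions. Two programmers could follow the same text and produce different curves, neither matching the endpoints listed.

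**Working it through.** **The plan's own figure.** Biopsy results states no number. The denominator used below is the 44 evaluable men in the SAP's Planned sample size, which can be reproduced with a one-sample normal approximation (null 70%, true rate 83.6%, one-sided alpha 10%, power 80%):

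n = [(1.2816 × √(0.70 × 0.30) + 0.8416 × √(0.836 × 0.164)) / (0.836 − 0.70)]² = 43.69, so 44.

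The point does not depend on this calculation, only on 44 as a denominator.

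**Groups.** The documents give none of these counts, so all are assumed. For one definition of a positive biopsy:
- k: positive at Month 3, not retreated, radical therapy before Month 12
- j: positive at Month 3, not retreated, no radical therapy, negative at Month 12
- r: positive at Month 3, retreated, clear at Month 12
- m: positive at Month 12, whatever the Month 3 result
- s: radical therapy before Month 12 without any positive biopsy

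With no other loss before Month 12, the cumulative incidence is the number of events divided by 44.

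| Reading | Month 12 cumulative positive rate |
|---|---|
| Secondary endpoint definition | (k + j + m)/44 |
| Month 3 left out, radical therapy competing | m/44 |
| Month 3 left in for everyone | (k + j + r + m)/44 |
| Month 3 left out, repeat with radical therapy as an event | (k + s + m)/44 |

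**Size per man.** Each man in k or j lowers the main curve by 1/44 = 2.3 points if Month 3 is left out. Each man in r raises it by 2.3 points if Month 3 is left in. For k = 1 to 6 and j = 0, the first gap runs from 1/44 = 2.3 to 6/44 = 13.6 points.

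**Example 1: k = 3, m = 4, others zero.** Definition: 7/44 = 15.9%. Month 3 out: 4/44 = 9.1%. Repeat analysis: 7/44 = 15.9%.

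**Example 2: add j = 1 and r = 1.** Definition: 8/44 = 18.2%. Month 3 out: 4/44 = 9.1%. Month 3 in for everyone: 9/44 = 20.5%. Repeat analysis: 7/44 = 15.9%. No planned output equals the defined rate.

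**Population.** If the k men leave the efficacy population because they have no Month 12 biopsy, they are neither events nor competing events. Example 1 then gives m/(44 − k) = 4/41 = 9.8%.

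**Which rule applies at Month 12.** The secondary definition reaches Month 12 for three of the four definitions. For whole-gland pattern 4/5 it starts at Month 24, so at Month 12 the only comparison is the primary rule, which fails the k men but does not by itself fail the j men.

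**The case against.** Several points on the other side are sound.

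- **Removal of Month 3 is an inference.** A reader might conclude that the SAP takes Month 3 out of the curves for every man. The text does not say so: its first sentence lists Month 3, and the last can be read as adding a table. This stands, and it is why the point is one of inconsistency.
- **The repeat analysis and the table show these men.** Counting radical treatment as an event recovers the k men, and Example 1 then returns the defined figure. Their Month 3 result is in the binary table, and their treatment is in the time-to-therapy analysis. So it would be wrong to infer that early failures are hidden. But the repeat recovers them at the date of radical therapy and mixes them with the s men. It does nothing for the j men, and the table does not carry a positive forward.
- **Retreated men may be analysed apart.** The Efficacy analysis section mentions a secondary analysis including retreated men, which could mean that the main curve excludes them. Leaving Month 3 in would then be harmless. The Efficacy population definition does not exclude them, however, so this reading cannot be relied on.
- **A secondary curve need not match the primary proportion.** A reader might infer a contradiction with the primary analysis. The primary rule governs only the primary proportion, so this is a difference in handling that deserves a statement.
- **The outputs are descriptive.** Protocol 10.4.2 attaches no test to them. This limits the consequence but does not settle how to compute the curves.

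**Conclusion.** The concern holds as an internal inconsistency. The SAP does not settle whether a Month 3 positive is an event in the cumulative frequency, and a single rule for all men fails either way: leaving Month 3 out loses the non-retreated positives, and leaving it in keeps retreated and cleared men as events. Both depart from the SAP's Secondary endpoints.

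The size is 2.3 points on the Month 12 curve per affected man at 44 men, and 2.3 to 13.6 points for an assumed one to six non-retreated positives. These figures assume no other loss before Month 12 and that the men are in the analysis set. If no such man occurs, the effect is nil. The documents do not support any particular count.

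The primary decision (35 or more responders of 44) is unaffected, since the primary analysis has its own rule for early pattern 4/5 followed by radical therapy.

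**What to change.** In the SAP, under Biopsy results:

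1. For men not retreated, count a positive Month 3 biopsy as an event at Month 3 for the matching definition, ahead of any later radical therapy.
2. For men retreated after Month 3, set the Month 3 result aside and count the first positive biopsy after retreatment.
3. Keep the Month 3 binary table as an additional output.
4. State that men with a positive biopsy before Month 12 and no Month 12 biopsy stay in the analysis set for these curves, despite the Month 12 data requirement in the Efficacy population. Without this, item 1 may not reach the men it is meant for.

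The cost is a few sentences and one derivation. No clinical rule changes. If Month 3 would otherwise have been left out, the curves will look slightly less favourable.

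The curves can still differ from the primary result, and the SAP should say why. Its missing-data section counts a missing Month 12 biopsy as a primary failure, which the curves do not. A non-retreated man who is positive at Month 3 and clear at Month 12 without radical therapy may be a primary success yet an event in the curve.

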#### **Initiation of additional therapy**

Additional prostate cancer treatment is defined as any treatment for prostate cancer other than TOOKAD® Soluble-VTP, including surgery, radiotherapy (external beam, brachytherapy, focused), high intensity focused ultrasound, cryotherapy, hormonal therapy for cancer, chemotherapy for cancer.

The time to initiation of therapy will be analyzed using Kaplan-Meier estimates, presented as a survival curve with corresponding 95% confidence intervals. Subjects who did not initiate any therapy will be censored at the time of study termination. The corresponding Kaplan-Meier curve will also be presented. As a sensitivity analysis, this analysis will be repeated excluding ablative therapies and hormonal therapy, that is, an analysis of time to radical therapy (surgery, radiotherapy). Tables and figures will be provided as appropriate.

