4 TRIAL DESIGN

4.1 Overall study design and plan

This is a single center, single-arm, open-label, 60-month follow-up phase IIb clinical trial. Men with localized prostate cancer will receive TOOKAD® Soluble -VTP treatment under general anesthesia. Prior to the TOOKAD® Soluble- VTP treatment, patients will undergo routine ultrasound examination in the operating room for morphometric description of the prostate and to facilitate accurate treatment guidance for the treatment with TOOKAD® Soluble- VTP. Treatment will then be applied to the prostate gland as a focal therapy, hemiablation procedure designed to destroy the lobe of the prostate gland that contains the Gleason score 7 (3+4) cancer. Afterwards, patients will be followed for 12 months with clinical evaluation, questionnaires on QOL, erectile and urinary functions, and PSA testing. In addition, treatment outcomes will be assessed based on prostate biopsy results at 3, 12, 24, 36, 48 and 60 months after the TOOKAD® Soluble treatment. All patients will undergo biopsy at 3 and 12 months after the TOOKAD® treatment. Thereafter, biopsy will be performed for cause per institutional standards. If the Month 3 biopsy is positive for any cancer patients will be allowed a single re-treatment by TOOKAD® Soluble VTP. However, patients with evidence of clinical deterioration on the same side such as worsening Gleason score, increased core involvement with cancer tumor grades on the 3-month biopsy and/or rising PSA will be withdrawn from the study and proceed with standard care. In addition, patients who experience treatment-related Grade 3-4 adverse events during their first treatment will not be re-treated at month 3, will be withdrawn and proceed with standard care if the month-3 biopsy contains cancer on the same or contralateral side, unless justification for continuing on study is specifically sought and approved from the IRB.

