5.5.3 Exit from the Study

Subjects will have the right to withdraw from participation in the study at any time, for any reason.

Subjects may be withdrawn from the study at the discretion of the Investigator only if continuation will jeopardise the subjects’ health and/or welfare. Every effort must be made to follow withdrawn subjects for safety reasons using the appropriate CRFs until the planned end of the study period.

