5.5.4 Subject withdrawal

The criteria for terminating participation in the study are detailed below:

1. Serious adverse event that is study-related (see definition further below), as recommended by the Investigator, patients with grade 3 or 4 adverse events following their initial treatment who have evidence of treatable prostate cancer on month 3 biopsy will not undergo re-treatment, will be withdrawn from the study and proceed with standard of care unless justification for continuing on study is specifically sought and approved from the IRB.
2. Subject withdrawal: at any time, a subject can withdraw from the study at his request or on the basis of the Investigator's clinical judgment.
3. Patients with evidence of clinical deterioration on the same side such as Gleason grade 5 cancer, more than 2 sextants including Gleason grade 4 cancer on the treated side on the 3-month re-biopsy will be withdrawn from the study and proceed with standard care.
4. Major protocol violation, defined as any violation that may impact the safety of a study subject.
5. Termination of the study by the Sponsor.

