#### **Time to additional radical therapy (Days)**

The time to additional radical therapy will be calculated from the date of treatment to the date of initiation of the first radical therapy. If a subject did not receive any additional radical therapy during the study then the time to additional radical therapy for this subject will be censored at the study termination date.

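### Time to additional therapy is censored at an undefined study termination, and the SAP does not say that therapy started after protocol withdrawal counts, so use of additional therapy may be understated

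*SAP*

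**What the plan says.** The SAP, Initiation of additional therapy, sets the method: "The time to initiation of therapy will be analyzed using Kaplan-Meier estimates, presented as a survival curve with corresponding 95% confidence intervals". Its censoring rule is "Subjects who did not initiate any therapy will be censored at the time of study termination". The derived variable for radical therapy (SAP, Time to additional radical therapy) uses the same date and opens with the condition "If a subject did not receive any additional radical therapy during the study", which suggests that only on-study therapy is an event. Neither section defines the termination date.

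Protocol 4.1 says that men with same-side deterioration at Month 3 "will be withdrawn from the study and proceed with standard care". Section 5.5.4, with different criteria for deterioration, says that men found so at the 3-month "re-biopsy will be withdrawn from the study and proceed with standard care". Both sections also withdraw men with grade 3-4 events (treatment-related, in 4.1) and cancer on the Month 3 biopsy, unless the IRB approves continuation. The synopsis (Treatment conditions) applies that IRB exception to progression as well.

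On follow-up after exit, Protocol 5.5.3 says: "Every effort must be made to follow withdrawn subjects for safety reasons using the appropriate CRFs until the planned end of the study period". Section 10.4.1 says that additional cancer therapies will be documented and sets no cut-off at withdrawal.

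The SAP's Efficacy analysis section applies the efficacy population to all efficacy analyses. That population requires data from the 12-month biopsy.

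**The concern.** Kaplan-Meier treats a censored man as having the same future risk as those still under observation. Here the protocol removes some men because their disease has worsened, and sends them to care in which additional therapy is likely. If they are censored at that moment and their later therapy is ignored, the curve gives them the lower risk of the men who stayed.

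Reading the date as the end of the trial avoids this but creates another problem. A man lost to follow-up, or withdrawn with unrecorded therapy, is kept in the risk set as therapy-free to a date on which nobody knows his status.

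Use of secondary therapy is a stated objective, and this curve is its main analysis. A reader will take it as the proportion of men spared further treatment.

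**Working it through.** **1. What the termination date can mean.** Both readings have support.
- *Individual exit:* Protocol 5.5.2 speaks of a subject being terminated from the study, and the SAP's Subject disposition section refers to early terminations with reasons.
- *End of trial:* Protocol 11.5, on the study termination visit, describes what happens when the study ends, and 5.5.4 item 5 is termination by the sponsor.
- The SAP uses a third rule for stage progression: censoring at the last on-study disease assessment.

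**2. Who is in the analysis.** A man withdrawn at Month 3 with no 12-month biopsy is outside the efficacy population, so he is excluded and not censored. Yet the SAP's missing-data section counts a missing Month 12 biopsy as failure in the primary analysis, so his status is not consistent across the SAP.

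**3. Size.** The plan states no event count or rate for this endpoint, so there is no figure to reproduce. The illustration uses:
- N = 50 treated men (protocol synopsis; 44 is the evaluable target).
- w = men withdrawn after Month 3, censored at Month 4 or starting therapy at Month 6 (assumed).
- m = later events in other men, spread over Months 12 to 60 (assumed).
- No other loss before Month 60 (assumed).

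With no other censoring, the product-limit estimate at Month 60 reduces to simple ratios:
- all therapy counted: (w + m)/N
- withdrawn men censored at exit, or excluded: m/(N − w)
- withdrawn men carried therapy-free to Month 60: m/N

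For w = 5, m = 5: (5 + 5)/50 = 20.0%; 5/45 = 11.1%; 5/50 = 10.0%.

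| w | m | Counted | Censored at exit or excluded | Carried to Month 60 | Shortfall, censored at exit (points) |
|---|---|---|---|---|---|
| 2 | 5 | 14.0% | 10.4% | 10.0% | 3.6 |
| 2 | 10 | 24.0% | 20.8% | 20.0% | 3.2 |
| 5 | 5 | 20.0% | 11.1% | 10.0% | 8.9 |
| 5 | 10 | 30.0% | 22.2% | 20.0% | 7.8 |
| 8 | 5 | 26.0% | 11.9% | 10.0% | 14.1 |
| 8 | 10 | 36.0% | 23.8% | 20.0% | 12.2 |
| 10 | 5 | 30.0% | 12.5% | 10.0% | 17.5 |
| 10 | 10 | 40.0% | 25.0% | 20.0% | 15.0 |

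Censoring at exit and exclusion coincide because the withdrawals precede every other event.

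**4. Dependence on what withdrawn men do.** The table assumes that all w start therapy. If only k do, the counted figure is (k + m)/N. With w = 5 and m = 5, k = 0 gives 5/50 = 10.0%, and k = 1 gives 6/50 = 12.0%, against 11.1% when censored at exit. The shortfall appears once withdrawn men are treated more often than those who stay, which is what withdrawal to standard care for deterioration suggests.

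**The case against.** The strongest reply is that the protocol already provides for most of the data. Section 5.5.3 asks for follow-up of withdrawn men to the planned end. Section 9.2 continues adverse event follow-up after additional treatment, 7.2 continues questionnaires through radical therapy, and 10.4.1 documents additional therapies. The censoring rule covers only men who started no therapy, so a withdrawn man whose therapy is recorded need not be censored at all. If that is the intention, and he is in the analysis set, the rule causes no bias.

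This stands as far as data collection goes. It does not settle the analysis. Follow-up under 5.5.3 is for safety, no section says that therapy after withdrawal is an event, and the radical-therapy variable refers to therapy during the study. Better capture also does not bring back men excluded for lack of a 12-month biopsy.

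Other limits on the concern also stand:
- The progression-based withdrawal rule is tied to Month 3. Later radical therapy (Protocol 6.4.11) is not said to cause withdrawal.
- Exits unrelated to cancer need not be informative, and censoring men who die untreated would push a Kaplan-Meier estimate of therapy use up.
- The objective is descriptive and untested, and the primary analysis does not depend on this curve.

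**Conclusion.** The point holds in a conditional form. The rule as written leaves the censoring date and the status of post-withdrawal therapy open. Under either reading the estimate may understate use of additional therapy when therapy after exit is unknown or not counted, and the efficacy population adds to this.

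In the illustration, 20% falls to 11% or 10%. Over the assumed 2 to 10 withdrawals and 5 to 10 later events, censoring at exit understates by about 3 to 18 percentage points. These figures rest wholly on assumed counts and on every withdrawn man starting therapy, so they show the scale and do not forecast it.

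A reader might infer that deteriorating men will in fact be censored just before their therapy, or that the bias must always favour the treatment. The documents support neither. The first needs the individual-exit reading. The second ignores that therapy recorded under 5.5.3 and 10.4.1, if counted in all treated men, would remove the bias.

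**What to change.** In the SAP sections Time to additional radical therapy and Initiation of additional therapy:
- Count any additional therapy started up to Month 60 as an event, including therapy started after withdrawal. For the radical-therapy analysis, do the same for radical therapy.
- Replace study termination with the last date on which the man's therapy status is known.
- State that these analyses include all treated men and are not limited to the efficacy population. Changing the date alone would not restore men without a 12-month biopsy.
- State that therapy status is collected as part of the post-withdrawal follow-up in Protocol 5.5.3.

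Optionally, add a sensitivity analysis that takes protocol withdrawal to standard care as an event on the withdrawal date. It should stay a sensitivity analysis, because withdrawal does not show that therapy was started.

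The cost is SAP wording, one item collected within follow-up already required, and a reported therapy-free rate that may be lower.
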